10.5 Futility monitoring in CTC website

The Department of Biostatistics will provide and maintain a website (“Clinical Trial Conduct”: <https://biostatistics.mdanderson.org/ClinicalTrialConduct/>) for futility monitoring for this study. The Clinical Trial Conduct website resides on a secure server, and access is gained through usernames and passwords provided to personnel responsible for enrolling patients and updating patient data. The website is accessed through a browser using secure socket layer (SSL) technology. Personnel responsible for enrolling patients on trials, which includes the principal investigator(s), research nurse(s), and data coordinator(s), will be trained by members of the Department of Biostatistics in the use

of the trial website; the importance of timely updating of follow-up times and recording of events will be emphasized in training.

10.6 Analysis method

Data analysis will be performed using SAS or S-plus, as appropriate. The median PFS time will be estimated by Bayesian posterior estimates, along with the 95% credible interval. Toxicity will be reported by type, frequency and severity. Highest toxicity grades per patient per course will be tabulated for adverse events and laboratory measurements.

Demographic and baseline laboratory results will be summarized using descriptive statistics, including means with standard deviations, or medians with ranges, histograms and box-plot. Fisher's exact test and Wilcoxon rank test will be used in the data analyses of categorical and continuous variables, respectively. Progression-free survival and overall survival functions will be estimated using the Kaplan-Meier method. The two-sided log-rank test will be used to assess the differences of time to events between groups, and Cox proportional hazards model will also be fitted to evaluate the association between time-to-event outcomes and tumor gene expressions. The correlation between pre- and post- therapy CT imaging results will be assessed through Spearman correlation and Wilcoxon signed rank test will be used to assess whether the change in CT imaging between pre- and post-therapy is statistically significant. In addition, logistic regression analyses will be performed to assess the association between CT imaging results or CA19-9 response (defined as >50% decrease from baseline) and tumor response.

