4. OBJECTIVES

PRIMARY

Determine the progression-free survival (PFS) of ramucirumab in advanced biliary cancers (intrahepatic cholangiocarcinoma, extrahepatic cholangiocarcinoma, and gallbladder cancer) who have received prior chemotherapy.

SECONDARY

- Determine the response rate (RR) and disease control rate (partial response + complete response + stable disease) of ramucirumab in advanced biliary cancers
- Determine overall survival (OS) of ramucirumab in advanced biliary cancers
- Evaluate the toxicity of ramucirumab in advanced biliary cancers

EXPLORATORY

- Correlate the carbohydrate antigen (CA) 19-9 response (defined as >50% decrease from baseline) with tumor response, PFS and OS
- Correlate baseline tumor gene expression profile with PFS
- Correlate pre- and post-therapy CT imaging to quantify iodine content, atomic numbers, and Z-values and correlate with response

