7. EVALUATION DURING STUDY

- Patients must begin Cycle 1 within 14 days of signing the informed consent document and after the screening assessments. Treatment will be administered by qualified and trained site personnel in a hospital, clinic, or other out-patient setting appropriate for chemotherapeutic infusions. All assessments should be performed within 72 hours of each specified time parameter, with the exception of Cycle 1 in which assessments must be conducted within 24 hours (except those noted), or if medical or scheduling conditions require a delay. Request of 20 unstained tumor slides of 5 to 10 microns thick will be sent at enrollment.

Day 1 of each cycle (except where noted)

- Inclusion/exclusion review (Cycle 1 only)
- Directed physical exam
- Vital Signs
- Measurement of weight (kg) and BSA calculation prior to dosing.
- ECOG Performance Status (see Appendix 1)
- Hematology: CBC with differential and platelet count

- Serum chemistries: glucose, creatinine, BUN, total bilirubin, AST, ALT, alkaline phosphatase albumin, LDH, total protein, and electrolytes (sodium, potassium, phosphorus, chloride, CO₂, magnesium, calcium). In patients with known Gilbert’s syndrome, it is recommended to perform a direct bilirubin and indirect bilirubin.
- CA 19-9
- Urinalysis
- AEs using the NCI CTCAE (<http://ctep.info.nih.gov>)
- Concomitant medication notation

Prior to Cycles 4, 8, 12, etc.

- In order to more precisely determine time to progression, the investigator is encouraged to obtain radiological assessments earlier if there is a strong clinical suspicion of disease progression, in order to either confirm or refute the clinical impression.
- Reassessment of the extent of tumor should be made by the same imaging methods used to establish baseline tumor measurements.

Table 7: Study Assessments (treatment cycle is 14 days)

Evaluation or Procedure	Screening ¹	Study Treatment	End of Treatment Evaluation ¹¹	30-day Post-Treatment Evaluation ¹² /Long Term Follow-up
		On or before Day 1 of each cycle		
Informed consent	X			
Medical History	X			
Physical Examination	X	X ^{3,4}	X	
Inclusion/Exclusion criteria	X			
Height	X			
Weight	X	X ^{3,4}	X	
Vital Signs (Blood Pressure)	X	X ^{3,4}	X	
ECOG Performance Status	X	X ^{3,4}	X	
Hematology ¹⁰	X	X ^{3,4}	X	
Biochemistry ¹⁰	X	X ^{3,4}	X	
Urinalysis ¹⁰	X	X ^{3,4}	X	
Serum or urine pregnancy test (for females of child-bearing potential)	X			
Tumor Tissue Collection	X ²			
Toxicity assessment	X	X ^{3,4}	X	X ⁸

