10. Hematology: complete blood count with differential. Chemistry: glucose, creatinine, BUN, total bilirubin, AST, ALT, alkaline phosphatase, albumin, LDH, total protein, and electrolytes (sodium, potassium, phosphorus, chloride, C02, magnesium, calcium). Tumor markers (CA19-9) as indicated. Tumor markers are performed every 2 cycles. In patients with known Gilbert's syndrome, it is recommended to perform a direct bilirubin and indirect bilirubin.
11. Within 10 days of decision to discontinue study treatment.
12. At 28-45 days from last dose of study medication.

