10.2 Primary efficacy endpoint

The primary endpoint is PFS, which is calculated as the time period from the date of treatment start to the date of disease progression or to the date of death, whichever occurs first, or to the last follow-up date if patients are alive without disease progression. It is expected that the median PFS time will be 3 months or more under this study treatment. If the trial continues to accrual of 60 patients and maintains sufficient follow-up to observe 35 events (PD/death) with a median PFS of 3 months, then the 95% credible interval for the median PFS would extend from 2.1 to 4.2 months.

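### Relating CA 19-9 response to PFS and OS needs a landmark or time-dependent method: an ever-responder log-rank test from treatment start is biased towards responders, by an amount the documents do not fix

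*Combined protocol and SAP*

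**What the plan says.** Section 4 lists as exploratory: "Correlate the carbohydrate antigen (CA) 19-9 response (defined as >50% decrease from baseline) with tumor response, PFS and OS".

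Section 10.6 assigns methods as follows.
- CA 19-9 response against tumor response: "logistic regression analyses will be performed to assess the association between CT imaging results or CA19-9 response".
- Gene expression: "Cox proportional hazards model will also be fitted to evaluate the association between time-to-event outcomes and tumor gene expressions".
- Time-to-event comparisons in general: "The two-sided log-rank test will be used to assess the differences of time to events between groups". The groups are not named.

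Section 10.2 defines PFS as "calculated as the time period from the date of treatment start to the date of disease progression or to the date of death". No time origin is given for OS; treatment start is assumed here.

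Section 6 sets 14-day cycles, restaging every 4 cycles and treatment until progression. CA 19-9 timing is stated in more than one way. Section 7 lists it under "Day 1 of each cycle (except where noted"). Footnote 10 to Table 7 says it is done as needed and then "Tumor markers are performed every 2 cycles". Section 7.1 has it as needed at the end of treatment. No visit or time is fixed for classifying a patient as a responder.

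**The concern.** CA 19-9 response is a post-baseline status. A patient whose first qualifying fall would come at a late draw can be called a responder only by staying progression-free until then. A patient who progresses sooner counts as a non-responder whatever the marker would have done. If the clock starts at treatment for both groups, responders are credited with event-free time that they needed in order to be classified.

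The result could be an apparent link between CA 19-9 decline and longer PFS or OS, reported as an early marker of benefit, when there is none. The PFS and OS parts of this objective also matter more than the tumor-response part. Section 2 reports a 0% response rate in the first 42 treated patients, so in that cohort the logistic regression has no responders to model.

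**Working it through.** **Which method applies.** This is a single-arm study, so the log-rank groups must be defined by patient characteristics. Logistic regression is tied to tumor response and Cox regression to gene expression. For CA 19-9 response against PFS and OS, the log-rank test is the only named method left.

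**Inputs from the documents.** Median PFS 3 months (10.2); median OS 6.31 months (Section 2, initial cohort); N = 60 (10.1); accrual 2.5 per month and scans every 4 × 14 days = 8 weeks (Section 6); draws every 2 × 14 days = 4 weeks (Table 7, footnote 10).

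**Check of the PFS model.** The plan gives no figure for the CA 19-9 comparison. Its own precision statement for 35 events and a median of 3 months is 2.1 to 4.2 months. An exponential model gives 3 × exp(±1.96/√35) = 2.15 to 4.18, which agrees.

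**Early events.** With exponential PFS, the share with an event by time t months is 1 − 2^(−t/3).
- 4 weeks (0.92 months): 1 − 2^(−0.307) = 19%.
- 8 weeks (1.84 months): 1 − 2^(−0.613) = 35%.

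**Null simulation.** Assumptions not in the documents: the rate and timing of CA 19-9 falls; all patients evaluable for CA 19-9; two-sided 5% level; 12 months of further follow-up. Progression is seen at 8-weekly scans, or PFS ends at death. OS is PFS plus an exponential post-progression time calibrated to the 6.31-month median. The first fall is independent of PFS and OS, can occur at up to 12 draws, and counts only if drawn before the PFS event. There were 4,000 trials per row. Cells show the rejection rate, with the apparent hazard ratio in brackets.

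| Chance of first fall per draw | Responders | PFS, log-rank from start | OS, log-rank from start | PFS, 8-week landmark | OS, 8-week landmark, progression-free only |
|---|---|---|---|---|---|
| 5% at every draw | 19% | 61% (0.47) | 41% (0.59) | 7.3% | 9.1% |
| 10% at every draw | 32% | 90% (0.37) | 69% (0.51) | 5.8% | 6.7% |
| 10, 8, 5, 3, 2, then 1% | 20% | 18% (0.68) | 12% (0.76) | 6.2% | 6.8% |
| 20% at first draw only | 20% | 4.7% (0.98) | 5.1% (0.98) | 6.7% | 7.0% |

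A separate simulation with the same scan and draw intervals and N = 60 gave 52-89% for PFS when falls can occur at any draw, 12-23% when they are mostly early, about 5% at the first draw only, and 4-7% with the landmark.

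In the first three rows essentially all log-rank rejections favour responders. The small excess over 5% with the landmark comes from small responder groups; only 1-2% of trials reject in favour of responders.

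**Time-dependent alternative.** For PFS, a test with CA 19-9 response as a time-dependent covariate rejects in 5.3-5.8% of trials across the four rows. For OS, the same test without allowance for progression still rejects in 7-28% when falls can occur at any draw, because sampling ends at progression.

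**The case against.** **The plan does not say that it will do this.** The log-rank sentence names no groups. Primary site, or the DNA-repair/FGFR cohort, would fit it too. A reader might infer that the plan prescribes this test for CA 19-9; the documents support that only by elimination. This limits the wording and not the remedy, since if the log-rank test is not meant, a stated objective has no method and Section 10.6 needs the same paragraph.

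**A spurious finding is not certain.** A reader might also infer that CA 19-9 decline is bound to look prognostic. The documents do not support that, because they give neither the response rate nor its timing. The first scan is at 8 weeks, so a draw at 4 weeks precedes nearly all recorded progression, and falls confined to that draw produce almost no bias. With other assumed inputs (30-60% latent responders, mean time to response 1-2 months, 15% of PFS events being deaths between scans), rejection at N = 60 is 7-32% if a draw on the scan day counts and 8-50% if it does not. Classifying by week 8 with 2-weekly draws gives 4-7%. All of this stands. But nothing in the plan restricts classification to an early draw.

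**The schedule may not conflict outright.** The Section 7 heading allows exceptions, which could accommodate the footnote. The footnote still gives two rules itself, so one statement is needed.

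**The objective is exploratory.** That is correct, and it limits the consequence.

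**Conclusion.** The point holds as a gap in specification with a known direction of bias. A comparison of ever-responders with other patients from treatment start favours responders, and the plan has no landmark, time-dependent covariate or classification time to prevent it.

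The size is conditional. Under the null, with 8-weekly scans, 4-weekly draws and N = 60, PFS rejection at a nominal 5% runs from about 5% (falls only at the first draw), through about 12-23% (mostly early falls), to about 50-90% (falls possible at any draw, 5-10% per draw). These figures rest on assumed CA 19-9 patterns and exponential PFS. The OS figures also assume treatment start as the origin.

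The primary PFS estimate, the sample size and both monitoring rules are untouched. The change is worth making because it is cheap and the comparison could otherwise mislead.

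**What to change.** Add a paragraph to Section 10.6.
1. Classify CA 19-9 response at a pre-specified landmark, for example 8 weeks from treatment start, when the first restaging is due. State it as a fixed time, since scans may move by a week.
2. For both PFS and OS, include only patients alive, progression-free and under observation at the landmark, and count time from it. Being alive is not enough for OS, because patients who have progressed are no longer sampled.
3. As an alternative for PFS, fit CA 19-9 response as a time-dependent covariate in a Cox model. For OS that model must also account for progression.
4. State the time origin for OS.

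Reconcile Section 7, footnote 10 to Table 7 and Section 7.1 into one CA 19-9 schedule, since the schedule decides who can be called a responder and when.

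The cost is a change of wording and one analysis. Patients with events before the landmark leave this comparison: about 35% by 8 weeks under exponential PFS with median 3 months, leaving roughly 0.65 × 60 = 39 patients before any censoring. The loss could be larger. The 44% disease control rate in the first cohort suggests that as few as about 0.44 × 42 ≈ 18 patients might remain there.

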11. DATA AND PROTOCOL MANAGEMENT

Designated research personnel must enter the information required by the protocol onto electronic Case Report Forms (CRFs). The University of Texas MD Anderson Cancer Center's Clinical Oncology Research (CORE) system, and the University of Texas MD Anderson Cancer Center's Protocol Data Management System[®](PDMS) CRF system will be used for this study. PDMS is a clinical research information management system. The PDMS CRF is an electronic document designed to record all the protocol-required information to be reported on each trial subject.

PDMS provides data entry templates as defined in the protocol. Laboratory results are automatically transferred from MD Anderson Cancer Center Laboratory Medicine's server to PDMS each morning. Users must have clearance through the MD Anderson Cancer Center Information Services Security Department in order to access PDMS. PDMS login is password protected. The Investigator is responsible for verifying and providing source documentation for all adverse events and assigning attribution for each event for all subjects enrolled on the trial.

12. CORRELATIVE STUDIES

All patients who sign consent for this study will provide consent for the collection of previously collected paraffin embedded tissue. Up to 20 unstained slides of 5 to 10

microns thick will be requested from the outside institution or prepared from the patient's tumor block, if applicable. Any residual tumor tissue above what is specified here will be returned to the sending institution. Collected paraffin embedded tissue will be handled by GI Medical Oncology research personnel. Only the PI and her authorized research staff will have access to the identifiable information from this study. All the samples extracted from the paraffin tissue used in this study will be coded and identifiers (name, medical record number) will not be present on any material that is undergoing analysis. Patient information and relevant data will be stored on password –protected institution computers behind the institution firewall. At the closure of this study all unused material will be either returned to the sending institution or destroyed.

When patients are enrolled, we will collect their pre-existing tissue biopsies, if available, for testing. The Oligo GEArray® Human Angiogenesis Microarray profiles the expression of 113 genes involved in modulating the biological processes of angiogenesis and will be investigated for correlation with outcome, include PFS. Archival tumor biopsy specimens will be used. This investigation will be performed at MD Anderson Core Facility. Recent data suggest that gene expression profiling may be predictive for response to anti-angiogenic agents³⁴. In addition, baseline VEGF-A in plasma was suggested as a possible predictive biomarker in a trial of bevacizumab in gastric cancer. Similarly, focal amplification of VEGFA in hepatocellular carcinoma predicted sensitivity to sorafenib both in animal models and in humans³⁵⁻³⁷.

Contrast enhanced dual-energy CT's that are triphasic or liver protocol will be utilized as standard of care imaging. This will consist of an arterial phase and a portal venous phase which will be performed on the 64-slice dual-energy CT scanner. All patients will be scanned in the cranio-caudal direction from the dome of the liver to the iliac crest during inspiratory breath-hold. Iodinated contrast medium will be intravenously administered via an automated dual-syringe power injector according to a body weight. The timing for the arterial phase scan will be determined by care bolus technique. AP scanning will start after the attenuation coefficient of abdominal aortic blood reached 100 HU. All images will be post processed to obtain the iodine and water images. Additional analysis will be done on the AW work station. This will allow for iodine content quantification pre- and post-therapy as well as calculation of atomic numbers and Z-values of the tumor in these patients^{38,39}. These quantifications will then be correlated with RECIST response measurements.

13. SAFETY REPORTING OF ADVERSE EVENTS

13.1 Adverse Event Reporting and Definitions

An adverse event is the appearance or worsening of any undesirable sign, symptom, or medical condition occurring after starting the study drug even if the event is not considered to be related to study drug. Medical conditions/diseases present before starting study drug are only considered adverse events if they worsen after starting study drug. Abnormal laboratory values or test results constitute adverse events only if they induce clinical signs or symptoms, are considered clinically significant, or require therapy.

Information about all adverse events, whether volunteered by the subject, discovered by investigator questioning, or detected through physical examination, laboratory test or other means, will be collected and recorded and followed as appropriate. Adverse events will be collected from the signing of the informed consent until 30 days after the last dose of study drug, or any time after that if the PI determines the event is related to the study drug.

The occurrence of adverse events should be sought by non-directive questioning of the patient at each visit during the study. Adverse events also may be detected when volunteered by the patient during or between visits or through physical examination, laboratory test, or other assessments. As far as possible, each adverse event should be evaluated to determine:

- The severity grade (mild, moderate, severe or grade 1-5)
- Its relationship to the study drug(s) (suspected/not suspected)
- Its duration (start and end dates or if continuing at final exam)
- Action taken (no action taken; study drug dosage adjusted/temporarily interrupted; study drug permanently discontinued due to this adverse event; concomitant medication taken; non-drug therapy given; hospitalization/prolonged hospitalization)
- Whether it constitutes a serious adverse event (SAE)

All adverse events should be treated appropriately. Such treatment may include changes in study drug treatment including possible interruption or discontinuation, starting or stopping concomitant treatments, changes in the frequency or nature of assessments, hospitalization, or any other medically required intervention. Once an adverse event is detected, it should be followed until its resolution, and assessment should be made at each visit (or more frequently, if necessary) of any changes in severity, the suspected relationship to the study drug, the interventions required to treat it, and the outcome.

Information about common side effects already known about drug can be found in the Investigators' Brochure or will be communicated between IB updates in the form of Investigator Notifications. This information will be included in the patient informed consent and should be discussed with the patient during the study as needed.

13.2 Adverse event attribution

- **Attribution** of the AE:
 - Definite – The AE *is clearly related* to the study treatment.
 - Probable – The AE *is likely related* to the study treatment.
 - Possible – The AE *may be related* to the study treatment.
 - Unlikely – The AE *is doubtfully related* to the study treatment.
 - Unrelated – The AE *is clearly NOT related* to the study treatment.

Adverse events for this protocol will be recorded using the Recommended Adverse Event Recording Guidelines for phase II protocols.

Recommended Adverse Event Recording Guidelines					
Attribution	Grade 1	Grade 2	Grade 3	Grade 4	Grade 5
Unrelated			Phase II	Phase II	Phase II
Unlikely			Phase II	Phase II	Phase II
Possible	Phase II	Phase II	Phase II	Phase II	Phase II
Probable	Phase II	Phase II	Phase II	Phase II	Phase II
Definitive	Phase II	Phase II	Phase II	Phase II	Phase II

The Investigator is responsible for verifying and providing source documentation for all adverse events and assigning attribution for each event for all subjects enrolled on the trial.

